8.3 Description of statistical methods

In non-inferiority trials, non-inferiority has to be demonstrated in the intention-to-treat and in the per protocol population. The primary analysis will be performed according to the intention-to-treat principles using the available case population which includes all participants with any primary end point data. Subsequently, a per-protocol analysis will be performed. EPG will be assessed by calculating the mean egg count from the quadruplicate Kato-Katz thick smears and multiplying this number by a factor of 24. The ERR will be calculated as:

$$ERR = 1 - \frac{\frac{1}{n} e^{\sum \log(EPG_{follow-up} + 1)} - 1}{\frac{1}{n} e^{\sum \log(EPG_{baseline} + 1)} - 1}$$

Geometric mean egg counts will be calculated for the different treatment arms before and at 14-21 days after treatment to assess the corresponding ERRs. Bootstrap resampling method with 5,000 replicates will be used to calculate 95% confidence intervals (CIs) for ERRs and the difference between the ERRs. CRs will be calculated as the percentage of egg-positive children at baseline who become egg-negative after treatment. Differences among CRs will be assessed by using unadjusted logistic regressions. In a subsequent analysis an adjusted logistic regression (adjustment for baseline infection intensity, age, sex, weight) will be performed.

Questionnaires on physical functioning and treatment satisfaction will be evaluated by creating summary scores by summing up and transforming the single question scores according to the following formula: [(actual raw score-lowest possible raw score)/(possible raw score range)]*100 [40].

Adverse events will be summarized in frequency tables and compared between treatment groups using descriptive statistics.

To assess differences in diagnostic performance of the different tools used as compared to the standard Kato-Katz microscopy (FECPAK-G2 and/or PCR) a readily available hierarchical Bayesian egg-count model will be applied to the individual level data.

A nonlinear mixed-effects (NLME) modelling will be used to determine pharmacokinetic parameters. Concentrations are measured with a validated LC-MS/MS method [20, 31]. Using NLME, the key population PK parameters will be calculated based on which an effect on the drug-drug interaction will be determined:

- C_{\max} maximal plasma concentration
- t_{\max} time to reach C_{\max}
- AUC area under the curve, from 0 to 24h and 0 to inf.
- $t_{1/2}$ elimination half-life

C_{\max} and t_{\max} will be observed values derived from the plasma concentration-time profile. Total drug exposure (AUC) and $t_{1/2}$ will be calculated with the NLME modeling software Monolix 2018R2 (Lixoft, Antony, France) using compartmental analysis. The elimination half-life will be estimated by the equation: $t_{1/2} = \ln 2/\lambda$, where λ (the elimination rate constant) will be determined by performing a regression of the natural logarithm of the concentration values during the elimination period. Primary PK parameters including absorption rate (k_a), volume of distribution (V), and clearance (CL) will be estimated utilizing NLME modeling.

The exact design of the sparse sampling scheme will depend on the results of current PK trials of our group. Optimization in nonlinear regression will be based on the Fisher information matrix M_F . Number of groups, subjects per group, samples per subjects and sampling times in each group will be adjusted to maximize the determinant of the Fisher matrix and hence minimizing the standard errors (SE < 25%).

9. Duties of the investigator

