Micro blood sampling by collecting blood from a finger prick has become the preferred method not only for molecular epidemiological studies but also for PK studies due to its minimal invasiveness, and simple and fast handling [18]. Furthermore, the results gained by this method have been repeatedly shown to correlate well with the standard venous blood sampling, which also holds true for ivermectin and albendazole and is currently under investigation for moxidectin by our group [19, 20]. A sparse sampling approach will be used in 60 participants, which allows to use only 4 samples per individual.

3. Trial objective and purpose

We designed a non-inferiority trial to show that co-administered moxidectin and albendazole is non-inferior compared to co-administered ivermectin and albendazole in adolescents aged 12-19 years on Pemba Island (Tanzania). From previous studies conducted by our group, we expect similar efficacies from the combination moxidectin/ albendazole compared to ivermectin/ albendazole [7, 8]. However, moxidectin might be advantageous in terms of the drug's longer half-life and in areas with possible emerging ivermectin resistance [17, 21]. This study will allow comparing the efficacy of the two available co-administrations and will provide further insights on the potential value of moxidectin/ albendazole. Our data will pave the way for possible large scale, multi country follow-up studies. As recommended for new combination therapies, we simultaneously assess superiority of the drug combinations compared to monotherapies.

The **primary objective** is to demonstrate that co-administered moxidectin (8 mg) / albendazole (400 mg) is non-inferior to ivermectin (200 µg/kg) / albendazole (400 mg) in terms of egg reduction rates (ERRs) against *T. trichiura* infections assessed by Kato-Katz at 14-21 days post-treatment in adolescents aged 12-19 years using a non-inferiority margin of 2 percentage-points.

The **secondary objectives** of the trial are:

- a) Efficacy assessments of combination therapies require demonstration of superiority against the respective monotherapies. Therefore, the trial has five different treatment groups: moxidectin (8 mg) / albendazole (400 mg) combination, ivermectin (200 µg/kg) / albendazole (400 mg) combination, albendazole (400 mg) monotherapy, ivermectin (200 µg/kg) monotherapy and moxidectin (8 mg) monotherapy.
- b) to determine the CRs of the drug regimens against *T. trichiura*

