4.1 Primary and secondary endpoint

Primary endpoint: the geometric mean based ERR of *T. trichiura* egg counts assessed by Kato-Katz microscopy pre-treatment and 14-21 days post-treatment.

Secondary endpoint: CR of *T. trichiura* as well as CRs and ERRs for *A. lumbricoides* and hookworm assessed by Kato-Katz at 14-21 days post-treatment. In addition, tolerability of treatment (AEs), infection status and intensity assessed at baseline and 14-21 days post-treatment by novel diagnostic tools (FECPAK-G2 and/or PCR), infection status and intensity derived by Kato-Katz at 5-6 weeks and 3 months post-treatment and PK/PD parameters of the study drugs will be assessed.

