8.1 Definition of primary endpoint

Egg reduction rate calculated from the geometric means of co-administered moxidectin/ albendazole and ivermectin/ albendazole against *T. trichiura* assessed at 14-21 days post-treatment is the primary endpoint in our study.

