8.2 Justification of number of trial subjects

For the primary analysis the trial is designed as 2 arm parallel group randomized-controlled trial. We test the primary hypothesis that the treatment combination moxidectin and albendazole is not inferior compared to ivermectin and albendazole. To determine the required sample size, we run a series of simulation using artificial data which behaved roughly in the same way as found by [7]. Assuming true ERR of 98% in both arms and 98.5% in both arms, we estimate that 160 participants are required in each group to be at least 90% sure that the limits of a two-sided 95% confidence interval will exclude a difference in favor of the standard group of more than 2 percentage points. To account for a potential loss to follow-up of 10% and including a safety margin of 20% to account for uncertainty in our assumptions underlying the simulations, we anticipate enrolling 210 participants in each combination treatment arm (arm A and B). Secondary hypothesis will compare monotherapies against the combinations. Assuming cure rates below 25% for albendazole and ivermectin and 40% for moxidectin monotherapy respectively, we need to enroll 20, 20 and 80 children, respectively, to identify a statistical significant difference with 85 to 90% power (arm C, D, E) [1, 5, 8, 39]. We thus aim to recruit 210 + 210 + 20 + 20 + 80 = 540 participants in total.

The suggested sample size of a maximum of 4 PK samples from 60 willing participants (10-15 per study arm) is sufficiently high to determine the population PK parameters and investigate drug-drug interactions with a sparse sampling scheme, considering that PK variability is moderate. A moderate PK variability is a reasonable assumption when dealing with adolescents.

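### The only written ERR formula (section 8.3) places 1/n outside the exponential, so it is not a geometric-mean ERR; in the combination arms it returns at least 99% for any reduction above about 3%.

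*Combined protocol and SAP*

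**What the plan says.** Section 4.1 defines the primary endpoint as "the geometric mean based ERR" for *T. trichiura*. Section 8.1 repeats this: "Egg reduction rate calculated from the geometric means of co-administered moxidectin/ albendazole and ivermectin/ albendazole". Section 8.3 then states how the ERR will be computed. In the extracted text, what follows the fraction sign is "1}{n} e^{\sum \log(EPG_{follow-up} + 1)} - 1" in the numerator and "1}{n} e^{\sum \log(EPG_{baseline} + 1)} - 1" in the denominator. In both, 1/n is a factor in front of the exponential and the exponent holds only the sum. The text after the formula returns to geometric means: "Geometric mean egg counts will be calculated for the different treatment arms before and at 14-21 days after treatment to assess the corresponding ERRs".

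No other ERR formula appears in the document. The ERR feeds the primary comparison of arms A and B (section 3), "using a non-inferiority margin of 2 percentage-points", with 95% confidence intervals from 5,000 bootstrap replicates (section 8.3). The sample size in section 8.2 rests on "Assuming true ERR of 98% in both arms and 98.5% in both arms".

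**The concern.** A geometric mean with an offset of 1 averages the logs before exponentiating: exp[(1/n) Σ log(EPG + 1)] − 1. The formula in 8.3 exponentiates the whole sum and divides by n afterwards. The prose and the formula therefore describe different quantities, and the formula is the more specific of the two.

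The primary conclusion is at stake. If the expression is followed, both combination arms show about 100% whenever counts clearly fall in both. The difference and its interval shrink to zero and lie inside the margin, so the error favours the hypothesis the trial sets out to prove. In the other direction, a rise in counts would give an absurd value: a 5% rise at n = 160 gives 1 − 1.05^160, about −245,500%.

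**Working it through.** **Inputs.** Section 8.2 requires 160 per combination arm and enrols 210, with 10% loss to follow-up (210 × 0.9 = 189). Monotherapy arms have 20, 20 and 80. The margin is 2 percentage points (section 3) and minimum baseline intensity is 48 EPG (section 5.2). The 210 is consistent with the stated allowances (160 × 1.3 = 208; 160 × 1.1 × 1.2 = 211.2). The 160 comes from simulations whose inputs are not given, so it cannot be reproduced.

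**What the formula computes.** Let Gb and Gf be the baseline and follow-up geometric means (offset 1 removed). Then exp[Σ log(EPG + 1)] = (G + 1)^n, and the formula gives

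ERR = 1 − [(Gf + 1)^n / n − 1] / [(Gb + 1)^n / n − 1] ≈ 1 − r^n, with r = (Gf + 1)/(Gb + 1).

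The two 1/n factors cancel and the −1 terms are negligible.

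**Small example.** Three participants each fall from 100 to 50 EPG. The geometric-mean ERR is 1 − 50/100 = 50%. The formula gives 1 − (51³/3 − 1)/(101³/3 − 1) = 1 − 44,216/343,432.67 = 87.1%.

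**Reduction at which the formula reaches 99%.** Ignoring the offset, solve (1 − reduction)^n = 0.01, so the threshold is 1 − 0.01^(1/n). The last column solves the full expression for baseline geometric means of 48 to 3000 EPG; the upper end of that range is assumed.

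| n | Arm | No offset | With offset |
|---|---|---|---|
| 160 | A, B required | 2.84% | 2.84% to 2.90% |
| 189 | A, B after 10% loss | 2.41% | 2.41% to 2.46% |
| 210 | A, B enrolled | 2.17% | 2.17% to 2.21% |
| 80 | E | 5.59% | 5.60% to 5.71% |
| 20 | C, D | 20.6% | 20.57% to 21.00% |

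The reduction here is the correctly computed geometric-mean reduction in the analysed sample.

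**At the planned efficacy, n = 160.** For a true ERR of 98%, log10(1 − ERR) from the formula is 160 × log10(0.02) = −271.8. For 50% it is 160 × log10(0.5) = −48.2. With the offset and an assumed baseline geometric mean of 100 to 1000 EPG, the 98% case gives about 10^-244 to 10^-269 and the 50% case about 10^-48. All display as 100%.

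**Effect on the non-inferiority decision.** This part is illustrative, because the document gives no egg-count distribution. The assumptions were a log-normal baseline with geometric mean 400 EPG and log SD 1.1, a floor of 48 EPG, follow-up log SD 1.3 among the uncured, and assumed cured shares (50% in arm B; 40%, 5% and 2% in arm A for the three rows). Each setting had 300 trials of 1,000 bootstrap samples at n = 160, with the formula evaluated on the log scale.

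| True ERR, A v B | Non-inferior, geometric-mean ERR | Non-inferior, formula as written |
|---|---|---|
| 96% v 98% | 2% | 100% |
| 50% v 98% | 0% | 99.7% |
| 30% v 98% | 0% | 64% |

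The last row is lower because, with a weak effect, some bootstrap samples show a rise and give very large negative values.

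A single simulated data set at n = 160 shows the same under similar assumptions (geometric mean 400 EPG, log SD 1.2, 20% and 40% zero counts, 5,000 replicates). Correct ERRs were 91.7% and 98.1%, a difference of −6.4 points (95% CI −10.7 to −3.5), which fails the margin. The formula as written gives a difference of 0 with interval 0 to 0.

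**The case against.** The strongest objection is that the error may not be on the page. The text was read from PDF by a program, and whether a small stacked fraction beside e is a factor or part of the exponent is easily misread. The two terms share one layout, so agreement between them is weak support. This stands as a reason to look at the source page before acting; if 1/n is in the exponent there, the point falls away.

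The second objection is that intent is not in doubt. Sections 4.1, 8.1 and the prose of 8.3 all name geometric means, and the expression contains every component of an offset geometric mean. A simulation in which every ERR is near 100% could hardly have led to a requirement of 160 per arm. This also stands: the point is an error in the formula and does not call the sample-size work into question.

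The third is that a literal calculation would not go unnoticed. In double precision (limit about 10^308) the baseline term overflows at n = 189 even at 48 EPG (10^319), so plain code would give exactly 100% or an undefined result. The thresholds above hold for evaluation on the log scale. That makes silent harm less likely, but it also shows that the expression cannot be used as written.

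Finally, the simulations rest on assumed egg counts, and the planned test of the monotherapy arms is on cure rates. Both are true. The thresholds for arms A and B depend on neither.

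**Conclusion.** The concern holds. As it reads, the only formula for the primary endpoint contradicts the endpoint's definition. In the combination arms it returns at least 99% once the geometric-mean reduction in the sample passes 2.2% to 2.9%, depending on n between 210 and 160. Followed literally, it makes non-inferiority close to automatic when counts clearly fall in both arms. The threshold figures need only n and a baseline geometric mean of at least 48 EPG; the decision rates are illustrative. The one condition is that the page itself shows 1/n outside the exponential. An analyst would probably see the slip, but the definition of the primary endpoint should not rely on that, so it must be corrected.

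**What to change.** Check the position of 1/n on the source page. If it is outside the exponential, replace the formula in section 8.3 with

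ERR = 1 − {exp[(1/n) Σ log(EPG_follow-up + 1)] − 1} / {exp[(1/n) Σ log(EPG_baseline + 1)] − 1}.

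This is one corrected line, with no change to procedures, sample size or participants. Section 9.1 requires modifications in writing and amendments to be signed by the sponsor/PI and submitted to the ethics committee, so the correction should go through that route rather than be made silently at analysis.

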4.3.6 Pharmacokinetic studies

The exposure-response correlation study will be performed in a maximum of 15 participants in the combination chemotherapy treatment arms and 10 participants in the monotherapy treatment arms, amounting to a subsample of 60 participants overall. This number of participants was determined to be representative of the study community taking into account the relatively low variability among PK values within a population. The absorption of all study drugs is known to be better after consumption of a high-fat meal, therefore study participants will receive a local high-fat breakfast before treatment [16]. Since PK population parameters of all study drugs are available [31], a sparse sampling approach can be applied to describe the PK profiles of the individual drugs upon co-administration as well as a potential interference between moxidectin or ivermectin and albendazole. Within a sparse sampling approach, instead of describing the PK profile for each participant separately, samples are allocated to different time points and individuals within the same treatment. Statistical inferences are performed to characterize the population-based PK profile of a specific treatment arm. This approach allows for a reduced number of samplings per participant and renders a PK characterization well tolerable. To this end, a small drop of blood from the fingertip will be taken. The sampling will be performed according to the following scheme:

- A maximum of 4 finger pricks will be done per participant throughout the whole PK study
- Of these 4 finger pricks per participant, a maximum of 3 pricks will be done on the same day
- The intervals between the pricks done on the same day will be at least 1h
- The whole PK study will be completed between day 0 and day 7

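### Section 8.3 takes Cmax and tmax as observed values, but it also assigns them to the NLME model, and the sparse sampling cannot give reliable observed peaks

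*Combined protocol and SAP*

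**What the plan says.** Section 8.3 makes two statements about how Cmax and tmax are obtained.

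- Introducing the parameter list (Cmax, tmax, AUC, half-life), a sentence that names NLME as the method says "the key population PK parameters will be calculated based on which an effect on the drug-drug interaction will be determined".
- After the list, it says that Cmax and tmax "will be observed values derived from the plasma concentration-time profile". By contrast, AUC and half-life "will be calculated with the NLME modeling software Monolix 2018R2". The absorption rate ka, volume V and clearance CL are also to be estimated by NLME.

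Section 4.3.6 describes the data: "instead of describing the PK profile for each participant separately, samples are allocated to different time points and individuals within the same treatment". It sets three limits. Each person's total is capped at four. The second limit reads "Of these 4 finger pricks per participant, a maximum of 3 pricks will be done on the same day". The third is a gap of one hour or more between samples taken within a day. Sampling runs from day 0 to day 7. The matrix is capillary blood dried on filter paper or Mitra sticks.

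The sampling times are not fixed. Sections 4.3.6 and 8.3 make them depend on other trials of the group, and Section 8.3 adds "Number of groups, subjects per group, samples per subjects and sampling times in each group will be adjusted" in order to optimise the Fisher information.

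**The concern.** The two statements in Section 8.3 give different rules for the same two parameters, and nothing else in the document chooses between them. Two analysts could follow the plan and report different Cmax and tmax values.

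The rule based on observed values also does not suit the data. With three or four samples per person, the largest measured concentration occurs at whichever scheduled time lies nearest the peak. The observed tmax is therefore one of the scheduled times, and the observed Cmax depends on how close that time was to the true peak.

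These parameters have a use in the trial. Under secondary objective g, albendazole in arms A and B is set against arm C, moxidectin in arm A against arm E, and ivermectin in arm B against arm D, with at most 10 to 15 people per arm. Section 2 justifies sampling the monotherapy arms by this interaction question. An effect of the schedule could be read as an interaction, or could hide one.

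**Working it through.** **The plan's own figure.** Two combination arms of 15 and three monotherapy arms of 10 give 2 × 15 + 3 × 10 = 60 participants, as stated. At 4 samples each, that is at most 60 × 4 = 240 samples: 60 per combination arm and 40 per monotherapy arm. The target of standard errors below 25% cannot be reproduced, because no sampling times or parameter values are given.

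**Inputs.** From Section 2: half-life 16-32 h for ivermectin and 491-832 h for moxidectin. From Section 4.3.6: the sampling limits above. Assumed, because the documents give no tmax and no albendazole half-life: a one-compartment oral model, shorter half-lives from 4 h upward, and true tmax of a few hours.

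**Formulas.** With ke = ln 2 / half-life, and concentration in units of absorbed dose / V:

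- C(t) = ka / (ka − ke) × [exp(−ke·t) − exp(−ka·t)]
- tmax = ln(ka / ke) / (ka − ke)

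**Step 1: one typical subject.** Take a half-life of 16 h and an assumed tmax of 4 h. Then ke = 0.6931 / 16 = 0.0433. Solving the tmax formula gives ka = 0.759 (check: ln(0.759 / 0.0433) / (0.759 − 0.0433) = 4.0 h). The true peak is C(4) = 0.8409.

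- First sample at 3 h, next at 24 h: C(3) = 0.8225, so observed/true = 0.8225 / 0.8409 = 0.978 and observed tmax is 3 h.
- First sample at 8 h: C(8) = 0.7475, so observed/true = 0.7475 / 0.8409 = 0.889 and observed tmax is 8 h.
- Two arms with the same drug and no interaction, one on each schedule: Cmax ratio 0.7475 / 0.8225 = 0.91, tmax 3 h against 8 h.

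**Step 2: a real delay under one common schedule (3 h, 24 h, day 7).** Halve ka to 0.380. True tmax moves from 4.0 h to 6.45 h, and true Cmax falls to 0.7561, a ratio of 0.7561 / 0.8409 = 0.90. The samples give C(3) = 0.6298 and C(24) = 0.3990, so observed tmax is 3 h in both arms. The observed Cmax ratio is 0.6298 / 0.8225 = 0.77. The delay is not seen in tmax, and the fall in Cmax is overstated.

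**Step 3: a pure exposure change under a common schedule.** Every concentration is multiplied by the same factor, so a 1.5-fold change is recovered as 1.50.

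**Step 4: with variability between people** (simulation; 50% in ka, 30% in ke, no assay error; half-life/tmax pairs 4/3, 8/4, 8/5, 12/5, 16/4 and 32/5 h):

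| Samples at | Geometric mean observed/true Cmax | Median observed tmax |
|---|---|---|
| 2, 4, 8, 24 h | 0.982-0.991 | 4 h |
| 3, 24, 168 h | 0.883-0.958 | 3 h |
| 8, 24, 72, 168 h | 0.559-0.954 | 8 h |

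The 0.559 belongs to the 4 h half-life alone; the other five pairs give 0.80-0.95 on that schedule. At 660 h, within the moxidectin range, the ratios are 0.991-0.999 on all three schedules.

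**Step 5: times staggered over individuals, as Section 4.3.6 intends** (second simulation; log-SD 0.3 for exposure, 0.4 for ka and 0.2 for ke, with 10% assay error; true tmax 2-8 h).

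- Observed tmax fell within 1 h of the true value in 7-36% of subjects.
- At a 16 h half-life (tmax 3-8 h), observed/true Cmax was 0.93-0.99 when everyone had dosing-day samples. It was 0.75-0.78 when one of three sampling groups was first sampled at 24 h.
- Different schedules in two arms, no interaction, 24 h half-life and tmax 5 h: spurious Cmax ratios of 0.89-1.11 and median tmax of 3 h against 6 h.
- Common schedule and halved absorption (true tmax 3 h to 5 h): median observed tmax did not move under 3 of 5 schedules.

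**The case against.** The strongest reply is that Section 8.3 already names NLME as the source of these parameters, so the sentence on observed values may be a leftover that no one will follow. That is possible, but the sentence is specific and separates Cmax and tmax from AUC and half-life, so it cannot be treated as inert. A related reply is that the profile meant is the pooled one for each arm. That would give one value per arm with no between-subject variation, and it would not be an observed individual peak.

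Three stronger readings are tempting, and the documents do not support them.

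- *A reader might infer that treatment arms will be sampled on different schedules.* Section 8.3 lets the number of groups itself be adjusted, while the trial has five fixed arms. Groups there more naturally means sampling groups within the population design. Different schedules are possible because the times are open, but they are not stated.
- *A reader might infer false Cmax differences of about 40%.* A gap of that size needs an assumed 4 h half-life and a first sample at 8 h in one arm only. A design optimised for a model that estimates ka is unlikely to choose that.
- *A reader might infer that Cmax would show the schedule and not the drug.* Step 3 shows that a pure exposure change survives a common schedule, and the bias is small when samples bracket the peak.

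Two further cautions stand. Assay error can push an observed maximum above the true peak: with 10% error, simulated moxidectin ratios were 1.04-1.09. Table 1 also shows visit columns and not PK sampling times, so the schedule of 3 h, 24 h and day 7 is only an illustration.

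**Conclusion.** The point holds as an internal contradiction with a practical consequence. Section 8.3 gives two incompatible sources for Cmax and tmax, and the observed-value rule does not fit the sampling in Section 4.3.6.

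The problem is clearest for tmax, which is confined to scheduled times whatever the drug. For Cmax the size depends on the schedule: about 1-2% low when samples bracket the peak and about 4-12% low for 3 h, 24 h and day 7. Larger shortfalls need a first sample that is late relative to the half-life. At moxidectin's half-life the bias is negligible.

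All magnitudes rest on an assumed one-compartment model and assumed tmax values; the flat moxidectin peak in particular follows from that model. The contradiction itself rests on the text alone. The matter is confined to secondary objective g and leaves the primary analysis untouched, but it should be corrected before the PK analysis.

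**What to change.** Amend Section 8.3 as follows.

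- Derive Cmax and tmax from the fitted NLME model, as individual empirical Bayes or population-simulated values, in line with what is already planned for AUC. This reconciles the two statements.
- Judge the interaction by the effect of co-administration as a covariate on ka, CL and V.
- State that raw observed maxima and their times are not compared between arms.
- Report shrinkage for the individual estimates.
- Replace plasma by dried capillary blood as the named matrix. This is a terminology correction only.

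The cost is wording. The model and its parameters are already planned, and no participants, samples or visits are added. The drawback is that model-derived peaks depend on the model and, with at most 4 samples per person, are pulled towards the population mean; hence the shrinkage report.

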The sparse sampling scheme will allow for a sufficient number of data points at a subsample of 60 participants to model the PK profiles of the drugs. The exact time points will have to be adapted according to PK data gathered during a current trial conducted by our group for the evaluation of the efficacy of moxidectin against *Strongyloides stercoralis*. Capillary blood ($\leq 30\mu\text{L}$, i.e. $10\mu\text{L}$ for ivermectin and albendazole and $30\mu\text{L}$ for moxidectin) will be collected by puncture with a finger prick. Two microsamples (duplicates) will be taken with one finger prick. Each time, the drop of blood (10 – $30\mu\text{L}$) will be directly transferred on filter paper or Mitra® sticks which should dry for approximately one hour. The dried sticks and filter paper will be transported to Swiss TPH, Basel, and stored at -20°C until analysis. The quantification of the study drugs will be performed using the validated liquid chromatography tandem mass spectrometry (LC-MS/MS) method as described elsewhere [20, 31]. Drug concentrations will be calculated by interpolation from a calibration curve with a lower limit of quantification of 1-5ng/ml. 7% of the sample duplicates will be analyzed for quality control, and the

measured concentrations will be used to determine between-run and overall precision and accuracy of the analysis.

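### Section 8.3 gives the elimination half-life two different estimators; the log-concentration regression does not suit the sparse PK design and should give way to the model-derived value

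*Combined protocol and SAP*

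**What the plan says.** Section 8.3 lists Cmax, tmax, AUC and t1/2 and gives their purpose: "Using NLME, the key population PK parameters will be calculated based on which an effect on the drug-drug interaction will be determined".

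On how t1/2 is obtained, the section makes two consecutive statements:

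- AUC and t1/2 "will be calculated with the NLME modeling software Monolix 2018R2 (Lixoft, Antony, France) using compartmental analysis".
- t1/2 equals ln2/λ, and λ "will be determined by performing a regression of the natural logarithm of the concentration values during the elimination period".

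The sentence after these assigns the absorption rate, volume (V) and clearance (CL) to NLME.

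Section 4.3.6 sets the data available. Each participant gives no more than four samples, and on their timing it says: "Of these 4 finger pricks per participant, a maximum of 3 pricks will be done on the same day". All sampling falls in the first week after dosing. The section explains that sparse sampling spreads time points over participants within an arm and does not build one profile per person. Concentrations come from "interpolation from a calibration curve with a lower limit of quantification of 1-5ng/ml". Neither section says how values below that limit are handled. Both leave the exact sampling times to PK results from other trials of the group.

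**The concern.** A compartmental fit already implies a half-life: with one compartment λ = CL/V, and with more it is the terminal rate constant. A separate regression of log concentrations can return a different number, and the plan does not say which is reported.

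The regression also asks for data that the design is not built to supply. It needs several quantifiable values in the elimination phase, whereas the plan collects few samples per person and relies on a population model to combine them.

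At stake is secondary objective (g), the drug-drug interaction. If the half-life estimate depends on how many samples fall below the quantification limit, it depends on exposure. A combination arm and a monotherapy arm could then differ in estimated half-life although elimination is the same in both.

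**Working it through.** **Inputs from the document.** At most 4 samples per participant, at most 3 on one day, window 168 h; up to 15 PK participants per combination arm and 10 per monotherapy arm; quantification limit 1-5 ng/ml (section 4.3.6). Half-lives of 16-32 h for ivermectin and 491-832 h for moxidectin (section 2). The plan states no computed half-life to reproduce. Its subsample size does reproduce: 2 × 15 + 3 × 10 = 60.

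**Step 1, per participant.** A slope needs at least two usable points, and three under a usual rule. With three samples around absorption on the dosing day, 4 − 3 = 1 elimination point remains and λ is undefined. In simulations of ivermectin (t1/2 24 h, illustrative times 2, 4, 8 and 168 h, three-point rule), 63-100% of participants had no value.

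**Step 2, pooled by arm, ivermectin.** Assumptions not in the plan: 15 participants; mono-exponential decline; two elimination samples each, drawn from 12, 24, 48 and 72 h; 40% between-person variability in starting concentration and 30% in λ; 15% assay error; values below the limit dropped. The estimate is ln2 divided by the pooled slope, shown as the median over simulated trials.

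| True t1/2 | Limit | Times | Start 20 | Start 40 | Start 80 ng/ml |
|---|---|---|---|---|---|
| 24 h | 5 ng/ml | 12-72 h | 48 h | 33 h | 27 h |
| 16 h | 5 ng/ml | 12-72 h | 37 h | 29 h | 23 h |
| 24 h | 5 ng/ml | 8, 12, 24, 36 h | 31-33 h | 24-25 h | 23 h |
| 16 h | 5 ng/ml | 8, 12, 24, 36 h | 29 h | 19 h | 16 h |

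The mechanism shows in the typical 72 h value. With a true half-life of 24 h, 72 h is three half-lives, so a start of 20 ng/ml leaves 20/8 = 2.5, a start of 40 leaves 5 and a start of 80 leaves 10 ng/ml. At a limit of 5, the low-start arm keeps late values only from people with unusually high concentrations, which flattens the line. In the first row, doubling exposure changes the estimate by 1 − 33/48 = 31% and then 1 − 27/33 = 18%, with elimination unchanged.

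At a limit of 1 ng/ml and 12-72 h sampling, the error stays within about 7% for a true half-life of 24 h or more, and is about +7% to +33% at 16 h.

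**Step 3, moxidectin.** The window covers 168/832 = 0.20 to 168/491 = 0.34 half-lives. At an assumed peak of 60 ng/ml nothing falls below the limit. Per participant, with one-exponential decline and times 4, 8, 24, 168 h or 4, 24, 72, 168 h, 11-24% have a non-positive slope and the median estimate is 0.68-0.87 of the truth: too short. Pooled, the estimate is about right (0.95-0.97). If a faster early phase is assumed (half-life 10-40 h, 20-60% of amplitude; times 4, 24, 72, 168 h), the pooled estimate falls to 0.15-0.80 of the truth.

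Albendazole was not simulated.

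**The case against.** The text can be read more kindly. It speaks of concentration values, not of measured ones; it says the key parameters come from NLME; and section 4.3.6 rejects describing each participant separately. On that reading, ln2/λ is only the definition of half-life inside the model-based analysis, and the per-participant failure concerns a method the plan does not intend. This has force: that the regression uses measured concentrations is an inference. But regressing model-predicted values would be redundant, since the fitted model already supplies the rate constant. The sentence still needs correcting.

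The second objection is that the sizes come from assumptions. This stands. Sampling times are deferred to a Fisher-information design aiming at standard errors below 25%; the plan states neither pooling nor dropping of low values; and 5 ng/ml is the unfavourable end of its range. Moving the assumed samples to 8-36 h removes most of the shift except at the lowest start. Nor does the plan assign an ivermectin sample to day 7, so the dilution by then (2^(168/32) = 38-fold to 2^(168/16) = 1,448-fold) shows no actual loss of data.

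A reader might infer that the regression always yields either nothing or a half-life that is too long, for every study drug. The documents do not support that. Moxidectin tends the other way or is roughly unbiased, ivermectin at a limit of 1 ng/ml is often close to the truth, and albendazole is untested.

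**Conclusion.** The point holds as a conflict between two adjacent rules, one of which is poorly matched to the design. That part rests on the text alone. The regression may be undefined for a participant, and may be biased when pooled, in a direction and by an amount that cannot be fixed in advance from the plan.

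The 48, 33 and 27 h sequence is one illustrative ivermectin scenario under the assumptions listed. It shows that an exposure difference alone can imitate a half-life difference; it does not predict what this trial will find.

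The consequence is confined to one of the four parameters listed for a secondary objective. Volume, clearance and absorption rate are assigned to NLME without ambiguity, and the primary endpoint and the 540 participants are untouched. A correction before analysis is warranted because it is cheap and because half-life feeds the interaction assessment.

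**What to change.** In section 8.3, delete the sentence that obtains λ by regression. Replace it with a statement that t1/2 is derived from the fitted NLME model: ln2 × V/CL for a one-compartment model, or ln2 divided by the terminal rate constant of the selected model otherwise. Add that values below the quantification limit enter the same Monolix fit as left-censored observations.

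The cost is one or two sentences. The model, V and CL are already planned, so no further samples, visits or analyses are needed.

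One limit remains after the change: with 0.20-0.34 half-lives observed, the moxidectin half-life will stay weakly identified, so it should be reported with its uncertainty.
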